### 4.2 Exclusion Criteria

1. Patients must not be currently receiving any chemotherapy agents (except Hydroxyurea)
  - a. Intrathecal ARA-C and intrathecal methotrexate are permissible (as they are not systemic and only isolated to the central nervous system).

- b. Patients cannot have received more than 3 prior lines of therapy for their hematologic malignancy. Patient may have previously had azacitidine or decitabine will be eligible to enroll on Arm A (MDS).
2. Patients must not be receiving growth factors.
3. Patients with a current second malignancy requiring systemic therapy, other than non-melanoma skin cancers, are not eligible. If a patient has had a prior second malignancy that is not currently requiring active treatment, the patient will be considered eligible.
4. Patients with uncontrolled high blood pressure, unstable angina, symptomatic congestive heart failure, myocardial infarction within the past 6 months or serious uncontrolled cardiac arrhythmia are not eligible.
5. Patients may not take any of the following medications while on study, but will be considered eligible if medication is discontinued 72 hours prior to first dose of Sirolimus:
  - Carbamazepine (e.g. Tegretol)
  - Rifabutin (e.g. Mycobutin)
  - Rifampin (e.g. Rifadin)
  - Rifapentine (e.g. Priftin)
  - St. John's Wort- may decrease effects of sirolimus by decreasing the amount of sirolimus in the body
  - Clarithromycin (e.g. Biaxin)
  - Cyclosporin e.g. (Neorla or Sandimmune)
  - Diltiazem (e.g. Cardizem)
  - Erythromycin (e.g. Akne-Mycin, Ery-Tab)
  - Itraconazole (e.g. Sporonox)
  - Fluconazole (e.g. Diflucan)
  - Ketoconazole (e.g. Nizoral)
  - Telithromycin (e.g. Ketek)
  - Verapamil (e.g. Calan SR, Isoptin, Verelan)
  - Voriconazole (e.g. VFEND) - May increase the effects of sirolimus by increasing the amount of this medicine in the body. Can take 72 hours after last dose of Sirolimus
  - Tacrolimus (e.g. Prograf) – May cause liver transplant rejection or serious side effects in patients on sirolimus.
6. Patients with known HIV positivity or AIDS-related illness are not eligible.
7. Patients with other severe concurrent disease which in the judgment of the investigator would make the patient inappropriate for entry into this study are ineligible.
8. Patients must not have received any investigational agents within 21 days of study entry.
9. Patients must not be pregnant or breastfeeding. Pregnancy tests must be obtained for all females of child-bearing potential. Pregnant or lactating patients are ineligible for this study due to the unknown human fetal or teratogenic toxicities of rapamycin. Males or females of reproductive age may not participate unless they have agreed to use an effective contraceptive method.
10. Patients who have uncontrolled infection are not eligible. Patients must have any active infections under control. Fungal disease must be stable for at least 2 weeks before study entry. Patients with bacteremia must have documented negative blood cultures prior to study entry.

#### **4.3 Subject Recruitment and Screening**

Subjects will be recruited from the practices of the Department of Medical Oncology, Thomas Jefferson University. The patients are not excluded based on gender, race or economic status. The patient must be at least 18 years of age. Patients who meet eligibility criteria will be invited by their physician to participate in the study. All therapeutic options will be discussed with the patient and the patient's questions will be answered to the patient's satisfaction. Patients will be asked to read, comment/ask questions about the study and then sign the informed consent form before study procedures are to take place.

Bone marrow biopsy/aspiration and/or tissue biopsy will be utilized to determine eligibility for the study. Screening laboratory work to be performed will include blood chemistries, pregnancy testing (if applicable) and a physical assessment, including a neurological exam. Patients will be offered an option to complete the standard of care chemotherapy treatment at the following Jefferson Health network

hospitals: Center City Hospital, Abington Hospital, Aria Hospital, Methodist Hospital and NJ Division (Kennedy) Hospital. All research related procedures are to be done at Jefferson Center City campus.

#### **4.4 Early Withdrawal of Subjects**

##### **4.4.1 When and How to Withdraw Subjects**

Subjects will continue on study treatment unless the following occurs:

1. Unacceptable toxicity. See section 3.2.2.1 for details.
2. Non-compliance by the patient with protocol requirements
3. Changes in medical status of the patient such that the patient no longer meets eligibility requirements or the investigator believes that the treatment is no longer in the patient's best interest.
4. Patient refusal
5. Disease Progression
6. Alternative therapy is started as per the discretion of the physician, for example, bone marrow transplant.

The discontinuation of study treatment will not constitute study withdrawal or study completion. In the event of a decision to discontinue treatment, the treatment phase will be considered complete and the follow-up phase will begin.

If a subject discontinues treatment and actively withdraws consent, no additional data will be collected.

### **5 Study Drug**

#### **5.1 Sirolimus**

Drug Name: Sirolimus

Other Names: Rapamycin, Rapamune®

Classification: Immunosuppressant Agent

Mode of Action: Rapamycin inhibits T-lymphocyte activation and proliferation in response to antigenic and cytokine stimulation. Its mechanism differs from other immunosuppressants.

Storage and Stability: Store at room temperature, 20°C to 25°C (68°F to 77°F); protect from light.

Dose Specifics: Assigned dose level. Patients will receive a 12mg loading dose of sirolimus. They will then receive a 4mg daily dose of sirolimus beginning 24 hours after the loading dose for the number of days indicated by protocol regimen.

Preparation 1 and 2 mg tablet

Route of Administration: All drug is to be taken by mouth. Doses should be given every 24 hours  $\pm$  2 hours. The drug should be consistently without food. Rapamycin will be given every 24 hours for number of days indicated by protocol regimen.

Incompatibilities: Diltiazem increases serum concentrations of sirolimus. Sirolimus serum concentrations may be increased with use of voriconazole, itraconazole, ketoconazole and fluconazole. Concurrent use of these drugs is contraindicated.

Availability: Available as Rapamune® 1mg tablet and 2mg tablets. Will be available through the Investigational Drug Services.

Side Effects

**Common** (21-100% Frequency) Immediate: Nausea, Vomiting Prompt: Within 2-3 weeks, prior to next course. Diarrhea, Hypertension, Increased creatinine Delayed: Any time after above.

Hypercholesterolemia, Hypertriglyceridemia

**Occasional** (5-20% Frequency) Immediate: Rash Prompt: Within 2-3 weeks, prior to next course.

Infections; edema; weight gain, arthralgia; tremor; acne; myelosuppression; fever; abdominal pain; myalgia; hypokalemia; hypophosphatemia Delayed: Any time after above. Stomatitis

**Rare** (< 5% Frequency) Hepatotoxicity Delayed: Any time after above. Hirsutism, Secondary Lymphoma, Inflammation of the lungs

Nursing/Patient Implications: Monitor blood pressure, and serum creatinine.

## 5.2 Azacitidine

Other Names: Vidaza

Classification: Hypomethylating Agent

Mode of Action: Azacitidine is a nucleoside analogue of cytidine that is thought to cause hypomethylation of DNA in rapidly dividing cells. Hypomethylation of the DNA of cancerous hematopoietic cells is thought to inhibit uncontrolled cell cycle by restoring the ability for differentiation and normal growth factor responses. The drug has little effect on non-proliferating cells.

Storage and Stability: Store unreconstituted vials at 25°C (77°F) with acceptable variation including 15° - 30°C (59°F-86°F). Reconstituted samples for subcutaneous injection are stable for up to 1 hour at 25°C (77°F) or for up to 8 hours between 2°C and 8°C (36°F and 46°F). Intravenous samples are stable at 25°C (77°F) but must be administered completely 1 hour after reconstitution.

Dose Specifics: 75mg/m^2 for 7 days in patients with normal renal function. Not studied in patients with reduced renal function. After 2 cycles, may increase dose to 100 mg/m^2 if no beneficial effect is seen and no other toxicity other than nausea and vomiting has occurred.

Preparation: 100mg: Injection, powder for suspension. Reconstitute with 4ml of sterile water for subcutaneous administration and 10ml of sterile water for intravenous. For intravenous usage, inject reconstituted solution in 50-100ml of normal saline solution or lactated ringers depending on desired final dosage/concentration.

Administration: I.V. infusions must administered within 1 hour of reconstitution and ideally should be administered in 10-40 minutes. Subcutaneous doses must be administered at least 1 inch from prior site of injection and doses greater than 2ml should be injected into two separate sites.

Compatibilities: Do not mix with Dextrose-containing fluids. Not compatible with hetastarch or fluids containing bicarbonate. Caution is urged when combining azacitidine with other immunosuppressing drugs.

Availability: Vials of powder for reconstitution, 100mg.

### Side Effects:

*Hematologic:* Anemia, febrile neutropenia, leucopenia, neutropenia, thrombocytopenia.

*Gastrointestinal:* Abdominal pain, constipation, diarrhea, nausea, vomiting

*General:* Fatigue, injection site reactions, pyrexia

*Infections:* Rhinitis, upper respiratory tract infection, urinary tract infection

*Metabolic:* Hypokalemia

*Renal:* Hematuria, serum creatinine elevation, renal failure

*Respiratory:* Dyspnea, exertional dyspnea, pharyngeal pain

*Skin:* Erythema, petechiae, pruritis, rash

**Nursing/ Instructions:** Assess results of laboratory tests for rising creatinine as azacitidine is primarily cleared by the kidneys. Use with caution in patients with chronic liver disease, as azacitidine has shown to worsen hepatic encephalopathy. Assess other pharmacological or herbal products patients may be taking for potential interactions. Infusion site must be monitored for signs of extravasation.

### 5.3 Treatment Regimen

#### 5.3.1 Chemotherapy

- Chemotherapy will consist of a sirolimus 12mg loading dose on day 1 followed by either 9 or 11 consecutive days of administration of sirolimus 4mg. If a split-dose schedule of azacitidine is followed, two additional doses of sirolimus will be given on days 11 and 12 of the 28 day cycles. If the alternate dose schedule is followed, sirolimus will be given on days 1-10. Concurrently, azacitidine 75mg/m^2 will be given on days 4-8, 11 and 12 with cycles repeating every 28 days. Alternately, seven consecutive days of infusion is allowable, i.e. Day 4-10. The schedule, with split dosing or consecutive day dosing, are both frequently used in the outpatient setting given depending on availability of weekend infusion services. Given evidence of near equal efficacy, the decision for consecutive day or split dosing will be decided on the basis of availability of services and the treating physician's discretion. Patients will be offered an option to complete the standard of care chemotherapy treatment at the following Jefferson Health network hospitals: Center City Hospital, Abington Hospital, Aria Hospital, Methodist Hospital and NJ Division (Kennedy) Hospital. All research related procedures are to be done at Jefferson Center City campus. After 2 cycles, may increase dose to 100 mg/m^2 if no beneficial effect is seen and no other toxicity other than nausea and vomiting has occurred.

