## 1.6 Dose Rationale and Risk/Benefits

Sirolimus will be given as follows: A loading dose of 12mg by mouth will be given on Day 1, and then 4mg by mouth every 24 hours for 9 doses, from Days 2 to 10 inclusive every 28 days if patient is getting consecutively dosed azacitidine, and 11 daily doses Days 2-12 if receiving split doses.

Duration of administration is until disease progression or toxicity requiring discontinuation of the drug.

Azacitidine will be given as follows: 75 mg/m^2/d for 5 consecutive days with two day break and then two additional consecutive days of treatment, i.e. from Day 4-8, 11 and 12 inclusive at least every 28 days. and no longer than 42 days Alternately, azacitidine will be given for 7 consecutive days, day 4-10 inclusive, at least every 28 days and no longer than 42 days.

After 2 cycles (per the current package insert), may increase dose to 100 mg/m^2 if no beneficial effect is seen and no toxicity other than nausea and vomiting has occurred.

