#### EXPERIMENTAL DESIGN SCHEMA:

DAY:	1	2	3	4	5	6	7	8	9	10	11	12
Sirolimus:	12mg	4mg	4mg	4mg	4mg	4mg	4mg	4mg	4mg	4mg	4mg	4mg
Azacitidine:				X	X	X	X	X			X	X
Azacitidine-Alt:				X	X	X	X	X	X	X		
PD:	X 			X 								
PK:				X 								

PD-Sample drawn before sirolimus dosing.

PD- Sample drawn before azacitidine administration

PK- Sample drawn before sirolimus and azacitidine administration

**Plasma Sirolimus (PK):** Sirolimus levels will be determined by commercially available assay. Rapamycin levels will be obtained **prior** to the dosing on Day 4. 3-4 cc of peripheral blood will be collected in a purple top (EDTA) tube to be sent to the local lab. Record the exact time that the sample was drawn along with the exact time that the last dose of drug was administered.

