## **5.4 Preparation and Administration of Study Drug**

Sirolimus will be purchased from Wyeth and then stored and dispensed from the Investigational Drug Service (IDS). It will be dispensed in pill bottles containing a full cycle's amount of Sirolimus and the labeling will contain explicit dosing instructions. Subjects may start a cycle as an outpatient and will self-administer their Days 1 and 2 doses at home or in the clinic prior to azacitidine administration. At time of enrollment, the subject, the subject will receive a pill diary to record time of pill administration. The subject will be asked to bring their pill bottle as well as their pill diary to the infusion center or hospital depending on location of treatment with azacitidine.

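### Both dosing schemas print one unqualified sirolimus row to Day 12, while the text ends sirolimus at Day 10 for the consecutive-day azacitidine schedule

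*Combined protocol and SAP*

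**What the plan says.** Section 1.6 sets the sirolimus course by azacitidine schedule. After the 12 mg loading dose on Day 1, it gives "4mg by mouth every 24 hours for 9 doses, from Days 2 to 10 inclusive every 28 days if patient is getting consecutively dosed azacitidine". The split schedule has a longer course in the same sentence: "11 daily doses Days 2-12 if receiving split doses". Section 5.3.1 repeats the rule. There the loading dose is "followed by either 9 or 11 consecutive days of administration of sirolimus 4mg". The section then ties the longer course to split azacitidine: "If a split-dose schedule of azacitidine is followed, two additional doses of sirolimus will be given on days 11 and 12 of the 28 day" treatment period. For the consecutive-day option the course is shorter: "If the alternate dose schedule is followed, sirolimus will be given on days 1-10". The Study Summary gives both possible last days, 10 or 12, without linking either to a schedule.

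The Experimental Design Schema appears twice, once in Section 1.6 and once in Section 5.3.1. Each copy has two azacitidine rows: the split schedule (Days 4-8, 11, 12) and the row labelled "Azacitidine-Alt" (Days 4-10). Above them is one sirolimus row, with 12 mg on Day 1 and 4 mg in every cell from Day 2 to Day 12. The numbered notes below each schema concern only the PD and PK samples. None of them restricts Days 11 and 12.

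On supply, Section 5.4 says of sirolimus: "It will be dispensed in pill bottles containing a full cycle's amount of Sirolimus". The same sentence goes on to require explicit dosing directions on the label.

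**The concern.** A reader who follows the consecutive-day row across the schema finds sirolimus still entered on Days 11 and 12, and nothing in the table says to stop at Day 10. The text says sirolimus does stop there. The table and the text therefore disagree for one of the two permitted schedules.

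This matters more than a slip in background text would, for four reasons.

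- Section 5.1 gives no number of days for the daily dose and defers to the protocol regimen. The regimen pages, schema included, are thus the source for orders and labels.
- The handover list for planned admissions in Attachment 3 gives the transfer date and the day of treatment, but not which azacitidine schedule the patient is on. The inpatient team then orders the sirolimus.
- The last sirolimus day determines when azoles may be used again (Sections 5.3.3 and 5.6, Attachment 3). Section 5.3.3 also lists fluconazole as recommended prophylaxis, so the date has practical use.
- Section 1.6 notes that an immunosuppressant may raise infectious toxicity and names infectious death as a signal to be watched closely.

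**Working it through.** **Inputs**

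- Loading dose 12 mg on Day 1, daily dose 4 mg afterwards (Sections 1.6 and 5.3.1).
- Consecutive schedule: daily doses on Days 2-10 (Section 1.6; Section 5.3.1 gives Days 1-10 including the loading dose).
- Split schedule: daily doses on Days 2-12 (Section 1.6; consistent with Section 5.3.1).
- Schema row: 12 filled cells, one of 12 mg and eleven of 4 mg (both copies).
- Azole restriction: 72 hours after the last sirolimus dose (Attachment 3; also Sections 5.3.3 and 5.6).

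**Step 1: reproduce the plan's own counts.** Days 2 to 10 are 10 - 2 + 1 = 9 daily doses. Days 2 to 12 are 12 - 2 + 1 = 11 daily doses. These are the 9 and 11 stated in Sections 1.6 and 5.3.1, so the text agrees with itself.

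**Step 2: confirm that azacitidine is not the source.** Split: 5 days (Days 4-8) + 2 days (Days 11 and 12) = 7. Consecutive: 10 - 4 + 1 = 7. Both azacitidine rows in the schema match the text.

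**Step 3: sirolimus per cycle**

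| Source | Doses | Total |
|---|---|---|
| Text, consecutive schedule | 1 + 9 = 10 | 12 + 9 × 4 = 48 mg |
| Text, split schedule | 1 + 11 = 12 | 12 + 11 × 4 = 56 mg |
| Schema, single row | 1 + 11 = 12 | 12 + 11 × 4 = 56 mg |

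The schema row equals the text for the split schedule. It matches the consecutive schedule only if the reader deletes Days 11 and 12.

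**Step 4: gap when the row is read literally for the consecutive schedule.** Doses: 12 - 10 = 2, or 2/10 = 20% more. Amount: 56 - 48 = 8 mg, or 8/48 = 16.7% more, per cycle.

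**Step 5: azole restriction.** 72 hours is 3 days. After a last dose on Day 10 it ends on Day 13; after a last dose on Day 12 it ends on Day 15. The shift is 2 days per cycle.

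For the split schedule both gaps are zero. The documents do not say what share of patients is on each schedule, so the number of patients to whom the gap could apply cannot be given.

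**The case against.** The strongest reply is that this is a missing qualifier, not a conflicting instruction. Neither schema says that its sirolimus row serves both schedules. The two azacitidine rows are alternatives on one grid, and the sirolimus row matches the first one listed. The rule is spelled out shortly before each copy of the schema, and no sentence anywhere supports Day 12 with consecutive dosing. Labels must carry dosing instructions. Dispensing is through the Investigational Drug Service, and patients treated at other network hospitals collect sirolimus at Center City (Attachment 2, note 21), so separate sites are not each working from the table. Finally, 56 mg per cycle is an exposure the protocol already plans for split-schedule patients.

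Most of this stands, and it rules out several stronger readings that a reader might infer:

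- *That the schemas prescribe sirolimus to Day 12 for both schedules.* They leave the row unqualified; they do not say so.
- *That patients on the consecutive schedule are receiving two extra doses.* Nothing in the documents shows that anyone doses from the schema alone.
- *That a dispensing error would run through a whole cycle of self-administered drug.* Sections 5.4 and 5.5 describe self-administration only for Days 1 and 2, and Section 5.5 assigns the later doses to inpatient nurses. Section 5.3.1 does mention outpatient treatment, so some later home dosing is plausible, but the documents do not describe it for Days 11 and 12.
- *That the efficacy or safety results are blurred.* The plan already mixes 48 mg and 56 mg courses by service availability and physician discretion (Section 5.3.1), and no effect of the schema on results is shown.

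The reply does not remove the discrepancy itself. A dosing table should be correct when read alone, and this one is not for one of the two schedules. The label instructions are not reproduced in the protocol, so the safeguard cannot be checked from the documents.

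**Conclusion.** The point holds as a minor internal inconsistency. Both copies of the schema carry an unqualified sirolimus row to Day 12 above two alternative azacitidine schedules. Sections 1.6 and 5.3.1 tie Days 11 and 12 to the split schedule and end sirolimus at Day 10 for the consecutive one. On a literal reading the difference is 2 doses, or 8 mg (56 against 48 mg), per cycle, and the azole restriction ends on Day 15 instead of Day 13. Staff using the schema alone could misdose; the documents do not show that anyone has.

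The size rests on two assumptions: that the reader applies the whole row to the consecutive schedule, and that doses are taken at about the same hour each day, so that 72 hours equals three calendar days. The designs in Section 7.1 are untouched: sample sizes, error rates and response cut-offs do not depend on this row. No view is taken here on which sirolimus days are clinically right.

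**What to change.** Reconcile the schemas in Sections 1.6 and 5.3.1 with the text of those sections and with the Study Summary. Either give each azacitidine schedule its own sirolimus row, or keep one row and add a footnote stating which schedule Days 11 and 12 apply to. In both cases show the days the investigators intend, and state the matching tablet count per cycle so that dispensing and labelling follow from the same table.

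It is worth checking notes 17 and 18 of Attachment 2 in the same pass. They treat Days 1-10 as on treatment and Days 11-28 as off treatment, although the text gives split-schedule patients both drugs on Days 11 and 12.

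The cost is an edit to one table that is printed twice, at the next amendment. No analysis or sample-size work is needed.

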#### EXPERIMENTAL DESIGN SCHEMA:

DAY:	1	2	3	4	5	6	7	8	9	10	11	12
Sirolimus:	12mg	4mg	4mg	4mg	4mg	4mg	4mg	4mg	4mg	4mg	4mg	4mg
Azacitidine:				X	X	X	X	X			X	X
Azacitidine-Alt:				X	X	X	X	X	X	X		
PD:	X 			X 								
PK:				X 								

PD-Sample drawn before sirolimus dosing.

PD- Sample drawn before azacitidine administration

PK- Sample drawn before sirolimus and azacitidine administration

**Plasma Sirolimus (PK):** Sirolimus levels will be determined by commercially available assay. Rapamycin levels will be obtained **prior** to the dosing on Day 4. 3-4 cc of peripheral blood will be collected in a purple top (EDTA) tube to be sent to the local lab. Record the exact time that the sample was drawn along with the exact time that the last dose of drug was administered.

#### Biologic Studies (PD)

**Pretreatment bone marrow aspirate:** 5-10 cc of Bone Marrow Aspirate in preservative-free heparin (green top) to be sent to the Stem Cell Core at the University of Pennsylvania. Aspirates should be drawn through a heparinized syringe. Peripheral Blood: 20 ml in a green top tube to be sent to the Stem Cell Core (if peripheral blast are  $\geq 5000/\mu\text{l}$  then a Bone Marrow Aspirate is not required). Both marrow and blood will be sent for any patient with a peripheral blast count less than  $5000/\mu\text{l}$  and greater than or equal to  $200/\mu\text{l}$ .

**Day 4 Bone Marrow:** 5-10 cc of Bone Marrow Aspirate in preservative-free heparin (green top) to be sent to the Stem Cell Core only if pretreatment blast count is  $\leq 200/\mu\text{l}$  otherwise 10cc peripheral blood may be substituted.

We will be determining the ability of oral sirolimus to inhibit mTOR in leukemic blasts. This will be measured by intracellular flow cytometry for phosphorylation of the downstream signaling target S6 ribosomal protein as a surrogate for mTOR activity. Flow results will be confirmed by Western blot as appropriate. The *in vivo* effects of sirolimus will be compared to a whole blood *ex vivo* rapamycin dose

response curve for each sample as well as to rapamycin levels obtained at the time of pharmacodynamic measurements. Finally, inhibition of S6 phosphorylation will be correlated with clinical outcome.

